#### Sample Size

With a sample size of 20 participants, we anticipate 99% power to detect a mean sweat chloride decrease of 10 mmol/L assuming a standard deviation of 9.7 mmol/L (Boyle et al., 2014; Vermeulen et al., 2017) under a one-sided 0.025 alpha-level t-test. With a higher standard deviation of 15 mmol/L, the power decreases to 81% to detect a mean decrease of 10, but we retain 98.9% power to detect the hypothesized mean decrease of 15 mmol/L.

SAEs and AEs will be tabulated using standard coding terms sorted by System Organ Class (SOC). The incidence of AEs will be tabulated by seriousness and severity. The number of SAEs and AEs will be

summarized as follows: (i) The proportion of subjects with at least one (S)AE, (ii) The average number of (S)AEs per subject, and (iii) The rate of (S)AEs per subject week of follow-up.

**Expected Outcomes** Subjects will be recruited by study investigators as above, including through the CF Foundation Therapeutic Development Network resource. Please note that based on considerable past experience conducting clinical trials involving CF subjects at both participating institutions, we do not have concerns regarding our ability to perform the patient-oriented study described here, or to propagate and characterize iPS cells (Crane et al., 2015; Mou et al., 2015; Hawkins et al., 2017; Jacob et al., 2017). The protocol will furnish one test of our hypothesis that thresholds of CFTR activity in differentiated iPS cells encoding partial function mutations *in vitro* or *in vivo* predict benefit following Trikafta™ *in vivo*. If a strong correlation can be established between Trikafta™ response *in vitro* and *in vivo* (e.g., FEV1) in both substudies, the clinical results will provide early evidence for possible usefulness of *in vitro* surrogate models in this setting.

**Scientific Rigor** All *in vitro* and *in vivo* studies will be conducted with appropriate “n” so that therapeutically relevant conclusions can be drawn. Multiple biologic or technical replicates will be performed and evaluated in blinded fashion by an experienced statistician. CFTR mutations are equally prevalent in both sexes, and we expect iPS cells studied in human subjects carrying partial function mutations will reflect male and female individuals equally.

**Summary** Many CF patients who might substantially benefit from new and precise modulator treatments do not have access to these drugs. Off-label prescribing of expensive new agents is often not reimbursed by third-party payers. This project will test new *in vitro* predictive thresholds using iPS cells for CFTR rescue *in vivo*, and furnish a body of knowledge relevant to such issues among individuals with rare or even private CF alleles. We will also specifically evaluate patients with CF encoding N1303K for evidence of clinical benefit attributable to Trikafta™.

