The study is an open-label clinical trial of orally-administered Trikafta™ in subjects with CF and carrying certain mutations that are without FDA approved modulator treatment. Subjects will be given the study drug elexacaftor 100 mg/tezacaftor 50 mg/ivacaftor 75 mg (2 pills once daily in the morning) and ivacaftor (150 mg) once daily in the evening, as the FDA-registered agent, Trikafta™. Dose and schedule will be identical to what has already been FDA-approved for the F508del CF genotype. Enrollment is planned at two centers, Emory University and University of Alabama at Birmingham. In Substudy 1, patients with residual CFTR function (based on sweat chloride < 80 meq/L or pancreatic sufficiency) will be tested. In Substudy 2, patients with CF encoding the N1303K variant will be enrolled as a “case in point” – emblematic of variants with *in vitro* evidence of Trikafta™ responsiveness who are not approved (i.e., not “on label” for the drug). iPSC-derived airway epithelial monolayers from these patients will be examined for their ability to predict FEV1 and sweat chloride response and other clinical endpoints. Our study will not significantly increase the risks (or decrease the acceptability of risks) associated with the use of Trikafta™ in CF.

Human subject participation will consist of a screening day (-28), day 1 (+/-2), day 7 (+/- 2) [phone call visit], day 14(+/-2), day 28 (+1/- 2) and day 56 (+/-2) follow up (wash-out). The visits will include patient history with concomitant medication review, physical exam, safety laboratory assessments (renal and liver panels, CBC/Diff, urinalysis), serum and urine pregnancy testing, CFTR genotype, spirometry, O2 saturation, sweat chloride test, ophthalmology exam in children, cutaneous punch biopsy and/or blood sample for iPSC derivation, EKG, drug accountability and questionnaire (CFQ-R assessment), and adverse event assessment.

We anticipate the screening and enrollment visit will require 4-6 hours to complete the informed consent, medical history, O2 saturation, concomitant medication review, physical exam, safety laboratory assessments (CBC/Diff, RENAL/LFT chemistry panel, and urinalysis), EKG, CFTR genotyping, questionnaire, serum pregnancy test for females, sweat chloride test, and spirometry.

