On day 1 (when subject returns), the visit will require approximately 6 hours to complete the concomitant medication review, adverse event assessment, interval medical history, physical exam, O2 saturation, safety laboratory assessments (CBC/Diff, RENAL/LFT chemistry panel, and urinalysis), questionnaire, sweat chloride, urine pregnancy test for females, spirometry, cutaneous punch biopsy (3mm) and/or blood sample, drug dispensing, and drug administration. The cutaneous punch biopsy may occur at any time between the Screening Visit and Day 1 based on dermatology clinic schedule availability.

- 1 Cutaneous 3 mm punch biopsy (performed here (and on day 56 if necessary to produce additional iPSC cells)): In this procedure, a circular blade is rotated from epidermis to subcutaneous fat, yielding a ~ 3 mm cylindrical core of tissue. Extending the skin perpendicular to the incision line allows for facile closure, which can typically be accomplished with a single suture. Pain is well-managed by local subcutaneous anesthetic. A small fibrotic scar can be minimized by linear closure of the biopsy. Significant pain, bleeding, or infection are very rare.

The subject will complete a phone call visit on day 7 (+/-2) that will require approximately 30 minutes to complete concomitant medication review, interval medical history, and adverse event assessment.

On day 14 (+/-2) the subject will return for a visit that will require approximately 5-6 hours to complete concomitant medication review, interval medical history, adverse event assessment, physical exam, drug dispensing and drug return, questionnaire, safety laboratory assessments (CBC/Diff, RENAL/LFT chemistry panel, and urinalysis), sweat chloride test, O2 saturation and spirometry. EKG will be performed on day 14.

On day 28 (+1/-2) we will conduct interval medical history, adverse event assessment, concomitant medications, physical exam, sweat chloride test, spirometry, O2 saturation, safety laboratory assessments (CBC/Diff, RENAL/LFT chemistry panel, and urinalysis), questionnaire, and drug return. This visit should require 4-6 hours to complete. This visit should occur no later than Day 29 since a 28-day supply of Trikafta™ will be provided.

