The 'wash-out' visit will be conducted on day 56 (+/-2) which will require approximately 4-6 hours to complete concomitant medication review, interval medical history, adverse event assessment, physical exam, safety laboratory assessments (CBC/Diff, RENAL/LFT chemistry panel, and urinalysis),

questionnaire, sweat chloride, urine pregnancy test for females, cutaneous punch biopsy (3mm) and/or blood sample, O2 saturation, and spirometry. The cutaneous punch biopsy may occur within ± 14 days of the day 56 visit based on dermatology clinic schedule availability.

Spirometry may be performed either pre- or post-bronchodilator at Screening. At all other visits, spirometry should be performed pre-bronchodilator. However, if patient is unable to withhold bronchodilator use at the Day 1 visit, then the spirometry assessment will be considered 'post-bronchodilator' and attempts should be made to collect spirometry post-bronchodilator at remaining visits.

In order for a spirometry assessment to be considered pre-bronchodilator, subjects should adhere to the following:

- Subjects should refrain from using short-acting bronchodilators (e.g., albuterol) or anticholinergic (e.g., ipratropium bromide [Atrovent®]) for more than 4 hours before the spirometry assessment.
- Subjects should refrain from using long-acting bronchodilator (e.g., salmeterol) for more than 12 hours before the spirometry assessment; and
- Subjects should refrain from using once-daily, long-acting bronchodilator (e.g., tiotropium bromide [Spiriva®]) for more than 24 hours before the spirometry assessment.

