#### 9. Study Discontinuation

Criteria for discontinuing the study intervention (e.g., halting rules), may include any monitoring test(s) and associated clinical decision point(s) which in the opinion of the clinical investigator, qualified designee, or Data Safety Monitoring Board are viewed as placing the patient at significant risk if Trikafta™ administration is to continue. This could include, for example (but is not limited to) worsening liver function or abnormalities associated with Trikafta™ administration. Discontinuation from Trikafta™ does not mean discontinuation from the study, and remaining study procedures should be completed as indicated by the study protocol. If a clinically significant finding is identified (including, but not limited to changes from baseline) after enrollment, the investigator or qualified designee, and/or Data Monitoring Committee (DMC) (also referred to as Data Safety Monitoring Board, DSMB) will determine if any change in participant management is needed. Any new clinically relevant finding will be reported as an adverse event (AE).

The data to be collected at the time of study intervention discontinuation will include:

- All measurements described for the day 56 follow-up/washout visit

Participants are free to withdraw from participation in the study at any time upon request.

An investigator may discontinue or withdraw a participant from the study for the following reasons:

- If any clinical adverse event, laboratory abnormality, or other medical condition or situation occurs such that continued participation in the study would not be in the best interest of the participant
- Disease progression which requires discontinuation of the study intervention
- If the participant meets an exclusion criterion (either newly developed or not previously recognized) that precludes further study participation
- Participant is unable to receive Trikafta™ for 3 days.
- Pregnancy
- Significant study intervention non-compliance

The reason for participant discontinuation or withdrawal from the study will be recorded. An attempt will be made to replace subjects who sign the informed consent form and receive Trikafta™, and subsequently withdraw, or are withdrawn or discontinued from the study.

A participant will be considered lost to follow-up if he or she fails to return for any scheduled visit and is unable to be contacted by the study site staff.

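### Adverse-event summaries pool four weeks on drug with about four weeks of wash-out, so the Substudy 2 rate per subject-week describes neither period

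*Combined protocol and SAP*

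**What the plan says.** The adverse-event analysis for Substudy 2 stands at the end of section 11, under that substudy's Sample Size heading. Events are coded by system organ class and tabulated by seriousness and severity. They are then summarised in three ways: "The proportion of subjects with at least one (S)AE, (ii) The average number of (S)AEs per subject", and third, "The rate of (S)AEs per subject week of follow-up". Follow-up is not defined there, and none of the three summaries is divided by period. For Substudy 1, section 11 plans counts and percentages or means and standard deviations. It states no person-time rate and no period split.

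Section 5 fixes the time on drug. Of the Day 28 visit it says: "This visit should occur no later than Day 29 since a 28-day supply of Trikafta™ will be provided". It then says: "The 'wash-out' visit will be conducted on day 56 (+/-2" days. That last visit again includes "concomitant medication review, interval medical history, adverse event assessment, physical exam, safety laboratory assessments", so adverse events are collected throughout the wash-out.

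Section 9 adds that stopping Trikafta "does not mean discontinuation from the study, and remaining study procedures should be completed as indicated by the study protocol". A subject who stops early can therefore contribute more off-drug than on-drug time.

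**The concern.** Verifying the safety of Trikafta in the enrolled patients is a secondary objective in the section 4 table. A reader of the safety tables will want to know how often events occur while patients take the drug. A rate over the whole eight weeks does not answer that.

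Two kinds of event have opposite meanings for the drug. An event on treatment may be toxicity. A worsening of CF symptoms after Day 28 may be loss of benefit. Pooled, they look the same.

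The trial has one arm, so the only comparison it offers for adverse events is each subject's time on drug against time off drug. The planned tables discard that comparison. For efficacy, the plan does respect the boundary: Substudy 2 measures change through Day 28, and the Substudy 1 mixed models treat Day 56 as its own time level.

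**Working it through.** The plan states no adverse-event rate and no subject-week total, so there is no figure to reproduce. The check asks how far the planned rate can lie from the on-drug rate.

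**Inputs**
- Time on drug: 28 days (section 5).
- End of follow-up: Day 56 (section 5).
- Windows in the section 5 text: +1/-2 days at Day 28, +/-2 days at Day 56.
- Substudy 2 sample size: 20 (section 11).
- k = off-drug event rate / on-drug event rate. This is not in the documents; it is an assumption, shown from 0 to 1.5.

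**Subject-weeks.** Total 20 x 8 = 160; on drug 20 x 4 = 80.

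**Off-drug share of follow-up.** Nominal: 28/56 = 50%. Treating the Day 28 visit as the end of drug, the extremes are (58 - 26)/58 = 55% and (54 - 29)/54 = 46%.

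**Ratio of the on-drug rate to the reported rate.** Let the on-drug rate be r and the off-drug rate kr. Expected events are r(T_on + k T_off), and the reported rate divides these by T_on + T_off. So

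ratio = (T_on + T_off) / (T_on + k T_off) = 2/(1+k) when the two periods are equal.

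The share of counted events that arise off drug is k/(1+k).

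| k | ratio | share of events off drug |
|---|---|---|
| 0 | 2.00 | 0% |
| 0.25 | 1.60 | 20% |
| 0.5 | 1.33 | 33% |
| 0.75 | 1.14 | 43% |
| 1 | 1.00 | 50% |
| 1.5 | 0.80 | 60% |

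With the window extremes, the ratio at k=0 runs from 54/29 = 1.86 to 58/26 = 2.23. At k=0.5 it runs from 1.30 to 1.38. The ratio does not depend on the number of subjects.

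**Illustration (invented counts).** With 12 on-drug and 6 off-drug events among 20 subjects, the on-drug rate is 12/80 = 0.15 per week and the off-drug rate is 6/80 = 0.075. The plan would report 18/160 = 0.1125, and 0.15/0.1125 = 1.33. The mean per subject would be 18/20 = 0.9, against 12/20 = 0.6 on drug. Now swap the counts to 6 on drug and 12 off drug. The reported rate is still 0.1125 and the mean still 0.9, although the on-drug rate has halved to 0.075. The planned summaries cannot tell these two results apart.

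**Early stopping.** Suppose one of 20 subjects stops at Day 7 and is followed to Day 56. On-drug time is 19 x 4 + 1 = 77 weeks, and the ratio at k=0 is 160/77 = 2.08. If four stop at Day 14, it is 16 x 4 + 4 x 2 = 72 weeks, and 160/72 = 2.22.

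**The case against.** Three stronger readings are tempting, and the documents do not support them.

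- A reader might infer that on-drug rates are diluted about twofold. That is the limit at k=0, when no event at all occurs in the wash-out. Any counted wash-out event brings the ratio below two, and above k=1 the direction reverses.
- A reader might infer that wash-out events are counted as Trikafta events. The plan tabulates events without attributing them to the drug, and does not call the rate an on-drug rate. What stands is that the two periods cannot be distinguished.
- A reader might work out an eightfold dilution for a subject who stops at Day 7 (56/7 = 8). That is one subject's denominator, again at k=0. The table reports a pooled rate, which moves only from 2.00 to 2.08. Continued follow-up is also not assured, because section 9 lets the investigator withdraw a subject from the study for an adverse event, or after three days without drug.

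There is also a case that the point matters little. The person-time rate is stated for Substudy 2 only. The proportion affected and the mean count have no time denominator to dilute, although they too pool the periods. No test or stopping rule uses the rate. The DSMB reviews safety data continually, but nothing says that it relies on this summary. All of that stands, and it limits the point to descriptive safety reporting.

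Finally, section 11 says that all analyses follow intention to treat, whatever the time on medication, and a rate over all follow-up fits that. A split by period does not conflict with it: every subject stays in, and the pooled table is kept.

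**Conclusion.** The point holds as a defect of descriptive safety reporting. On the plain reading of follow-up, the Substudy 2 rate mixes roughly equal amounts of on-drug and off-drug time and estimates neither rate. The event counts in both substudies have the same lack of separation.

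The size and direction of the error depend on k. Over the assumed range of 0 to 1.5, the on-drug rate is between 2.0 and 0.8 times the reported rate, and it equals the reported rate when events are equally frequent in both periods. These figures assume the nominal 28 and 56 days, with all subjects completing both periods. The planned tables would not let a reader recover k.

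The efficacy conclusions are not affected. The change is worth making because safety is a stated objective and the remedy is cheap.

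**What to change.** In section 11, define follow-up for adverse events and add an on-treatment window. In both substudies, tabulate AEs and SAEs separately for:

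- on-treatment time: first dose to the subject's actual last dose, plus a residual window stated in advance;
- post-treatment time: from the end of that window to Day 56.

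Give each period its own event counts, number of subjects affected and subject-weeks. Keep the pooled table as a supplement.

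The cost is wording, a few more table shells, and smaller counts in each period. The schedule lists adverse-event assessment and drug accountability by visit, but the documents do not state that onset dates and last-dose dates are recorded. Confirm that the case report form captures both.

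One related item needs reconciling. The schedule of events in section 5 has a mark in the drug-administration row at the Day 56 column, while the text of that section describes Day 56 as wash-out after a 28-day supply. Unless the mark is a fault of PDF extraction, the two must be brought into agreement, because on-drug time depends on it.

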## 12. Confidentiality:

- Participant confidentiality and privacy will be strictly held in trust by the participating investigators, their staff, and others responsible for the intended interventions. This confidentiality is extended to cover testing of biological samples and other tests in addition to the clinical information relating to participants. Therefore, the study protocol, documentation, data, and all other information generated will be held in strict confidence. No information concerning the study or the data will be released to any unauthorized third party without prior written approval.
- All research activities will be conducted in as private a setting as possible.
- The clinical investigators, other authorized representatives, representatives of the Institutional Review Board (IRB), or regulatory agencies may inspect all documents and records required to be maintained by the investigator, including but not limited to, medical records (office, clinic, or hospital) and pharmacy records for the participants in this study. The clinical study site will permit access to such records.
- The study participant's contact information will be securely stored at each clinical site for internal use during the study. At the end of the study, all records will continue to be kept in a secure location for as long a period as dictated by the reviewing IRB, Institutional policies, or other requirements.
- Study participant research data, which is for purposes of statistical analysis and scientific reporting, will be transmitted to and stored securely. This will not include the participant's contact or identifying information. Rather, individual participants and their research data will be

identified by a unique study identification number. The study data entry and study management systems used by clinical sites research staff will be secured and password protected. At the end of the study, all study databases will be de-identified and archived by the PI. With regard to other patient related aspects of confidentiality, all interviews and procedures will be held in a private room.

- Identifiers will be destroyed 3 years from the date of the Federal Financial Report (FFR).

